9.2.2. Intraocular Pressure (IOP)

Applanation tonometry (preferable Goldman) will be used for IOP measurements, where the value recorded on the eCRF is an average of 3 measurements. On Day 1, this assessment will be performed pre- and post-administration of study treatment.

A summary table presenting the observed values and changes from baseline in IOP (mmHg) will be presented by treatment group for the Safety population. Changes from baseline to each scheduled post-baseline visit, as well as the Day 1 post-administration of study treatment, will be presented.

The number and percentage of eyes with an IOP measurement > 21 mmHg at any postadministration assessment will be presented for each treatment group. Incidence will be summarized through Day 7 and month 12.

Additionally, the number and percentage of eyes with an IOP measurement meeting any of the IOP elevation criteria at any post-administration assessment and by visit will be presented by treatment group for the Safety population. The IOP elevation criteria include:

- Increase in IOP from baseline of > 5 mmHg
- Increase in IOP from baseline of $\geq 12 \text{ mmHg}$
- IOP measurement > 25 mmHg
- IOP measurement > 30 mmHg

IOP data will be presented in a listing.

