- 12. Following the injection, monitor the subject for elevation in intraocular pressure and for endophthalmitis. Determine IOP (recorded as a mean of three measurements) within 10 to 30 minutes following the injection. Prescribe a topical antibiotic for the subject to selfadminister 4 times per day for 3-5 days. Instruct the subject to report without delay any symptoms suggestive of endophthalmitis.

13. Contact the subject on the next day to determine the subject's ocular condition and to identify any complaint or adverse event.

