3.2. Study Endpoints

The primary utilization and safety analyses of the inserters will be conducted at Day 7; safety analyses of the FAI insert will be conducted at Day 7 and Month 12. Analyses will be based on individual eyes.

Evaluation of Mk II inserter and Mk I inserter

Utilization evaluation (based on individual eye):

The primary utilization endpoint is defined as the proportion of intravitreal insertion procedures that are assessed by the Investigator as satisfactory. A satisfactory procedure is defined as one receiving a score from the Investigator as either Very Easy (VE), Easy (E), or Routine (R), according to the following categories:

- Very Easy (VE)
- Easy (E)
- Routine (R)
- Difficult (D)
- Very Difficult (VD)

Secondary utilization endpoints include:

- Clarity of the Instructions for Use, as assessed by the Investigator
- Differences between observed procedure and instructions for use, as assessed by an Observer

Safety evaluation (based on individual eye):

Safety will be evaluated over one period: Day 1- Day 7, and will include:

• Ocular adverse events, including: procedure-related adverse events, IOP increase/decrease, medications/procedures required to treat adverse events, clinically significant ocular changes

Evaluation of the FAI insert

Safety will be evaluated for two periods: through Day 7 and through Month 12. Descriptive statistics will be used to present the results of all safety evaluations and will include:

- Ocular adverse events (base on individual eye), including: IOP increase/decrease, medications/procedures required to control elevated/low IOP, development or worsening of cataract, cataract-related procedures, clinically significant ocular changes
- Systemic adverse events

4. General Statistical Considerations

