When count data are presented, the percentage will be suppressed when the count is zero in order to draw attention to the non-zero counts. A row denoted "Missing" will be included in count tabulations where specified on the shells to account for dropouts and missing values. For by treatment summaries, the denominator for percentages will be the number of eyes in each category in that treatment within the analysis population of interest, unless otherwise specified. For summaries for all subjects for data summarized at the subject level, the denominator for percentages will be the number of subjects who have at least one eye within the analysis population of interest, unless otherwise specified.

Unless otherwise specified, baseline will be defined as the last non-missing evaluation prior to or on the date of treatment injection (Day 1). The study day will be calculated as assessment date – date of treatment injection (Day 1) + 1. Study day for non-ocular events and assessments will be determined using the date of treatment in the first treated study eye. Study day for ocular assessments for the first treated eye will be determined using the date of treatment in the first treated study eye. If the second eye is also treated, study day for the ocular assessments in that eye will be based on the date of treatment in that eye. If the second eye is not treated, study day for ocular assessments in that eye will be based on the date of treatment in the treated study eye.

For all utilization and safety analyses, analysis visit windows will be used for assigning assessments to an analysis visit, as follows:

Scheduled Visit	Target Day	Visit Window (Days)		
Screening	-60 to 0	Not applicable		

Day 1	1	Not applicable
Day 7	7	4 to 10
Day 28	28	14 to 42
Month 3	90	69 to 111
Month 12	360	332 to 388

Only those assessments which are assigned to an analysis visit will be included in the summary tables and figures which are presented by visit. If there are multiple assessments assigned to the same visit window, the observation to be used for analysis will be determined as follows:

If there is only one observation falling into a defined visit window, then that observation will be flagged for inclusion in by-visit analyses.

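### The Month 12 count of eyes with IOP above 21 mmHg includes the reading taken 10 to 30 minutes after injection with no way in the table to separate it, and the IOP baseline rule does not name the pre-injection value

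*SAP*

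**What the plan says.** **The reading.** SAP 9.2.2 says of IOP: "On Day 1, this assessment will be performed pre- and post-administration of study treatment". Protocol 9.7.3.1 (Mk I) sets the time: "Determine IOP (recorded as a mean of three measurements) within 10 to 30 minutes following the injection". Protocol 9.7.3.2 has the same step for Mk II.

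**The counts.** SAP 9.2.2 has two sets of threshold counts.
- Eyes with IOP above 21 "mmHg at any postadministration assessment will be presented for each treatment group". For this threshold, "Incidence will be summarized through Day 7 and month 12".
- Eyes meeting any of four IOP elevation criteria (rise > 5 mmHg, rise ≥ 12 mmHg, value > 25 mmHg, value > 30 mmHg): those meeting the "criteria at any post-administration assessment and by visit will be presented by treatment group for the Safety population".

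**The change table.** "Changes from baseline to each scheduled post-baseline visit, as well as the Day 1 post-administration of study treatment, will be presented".

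**The periods.** In SAP 3.2 inserter safety covers Day 1 to Day 7 only. For the insert, "Safety will be evaluated for two periods: through Day 7 and through Month 12". SAP 3.1 assigns the Month 12 analysis to insert safety, and SAP section 4 puts everything in the database into it.

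**Baseline.** SAP section 4 gives a default, to apply unless a section says otherwise: "baseline will be defined as the last non-missing evaluation prior to or on the date of treatment injection (Day 1").

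**The concern.** The Month 12 tables are the plan's account of insert safety. Protocol 5.2.3 expects elevated IOP to be among the most frequent adverse events, so a reader will look for an IOP rate there. A reading taken minutes after a needle has entered the eye may reflect the injection and not the steroid. The SAP recognises this for adverse events: section 9.1.9 reviews events in the first 7 days for relation to the procedure and names raised IOP as an example. The measured-IOP counts have no such step.

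The 21 mmHg threshold is the most exposed. It is the lowest absolute threshold, it equals the entry limit in Protocol 8.2 (criterion 9), so a small rise can cross it, and it is the only criterion with no by-visit display. The inserters use different needles (25 and 27 gauge, Protocol 5.4.3). If they differed in immediate rises, the difference would carry into the 12-month comparison of groups.

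The baseline definition matters because two of the four further criteria, and every change-from-baseline row, depend on which Day 1 value is used.

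**Working it through.** **1. Which readings enter the count.** The Day 1 post-administration IOP is a planned assessment in SAP 9.2.2. The > 21 mmHg count takes any post-administration assessment. No text excludes Day 1, and both reporting periods begin there. So one value above 21 mmHg at 10 to 30 minutes makes an eye elevated through Month 12, whatever follows.

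**2. Size.** The documents state no IOP rate, so there is no figure to reproduce and the rates below are assumptions. Let *s* be the proportion of eyes above threshold at the immediate reading and *p* the proportion above it at any later assessment.

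- Inclusive proportion under independence: 1 − (1 − s)(1 − p).
- Excess over the later proportion: s(1 − p).
- Bounds on the inclusive proportion under any dependence: max(s, p) to s + p.

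Inclusive proportion under independence:

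| s | p = 10% | p = 20% | p = 30% |
|---|---|---|---|
| 5% | 14.5% | 24.0% | 33.5% |
| 10% | 19.0% | 28.0% | 37.0% |
| 20% | 28.0% | 36.0% | 44.0% |
| 30% | 37.0% | 44.0% | 51.0% |

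The excess runs from 0.05 × 0.70 = 3.5 points to 0.30 × 0.90 = 27 points. Eyes counted only because of the immediate reading make up 3.5/33.5 = 10% to 27/37 = 73% of the total. At s = 10% and p = 20%, the count in 30 eyes is 0.28 × 30 = 8.4 instead of 0.20 × 30 = 6.0, with bounds of 20% to 30% on the inclusive proportion. If every eye with an immediate rise is also elevated later, the excess is zero.

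**3. Effect of one eye.** With the planned 10 Mk I and 20 Mk II eyes, one eye elevated only at the immediate reading moves its group's proportion by 1/10 = 10 points or 1/20 = 5 points.

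**4. Can the Day 7 column be subtracted?** Not exactly. Take s = p = 20%, independent, with no other elevation by Day 7. The Month 12 count is 36% and the Day 7 count 20%. The difference is 16%, but later elevation is 20%. The missing 0.20 × 0.20 = 4 points are eyes elevated at both times.

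**5. The other four criteria.** Their by-visit display lets a reader see elevation at the later visits, so the problem is smaller. Two gaps remain. The SAP does not say that this display gives the Day 1 post-administration reading its own row. Also, by-visit counts do not give the number of distinct eyes elevated after Day 1, since one eye may appear at several visits.

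**6. Baseline.** The pre- and post-injection readings share a date. The last non-missing value on or before that date is then the post-injection one. The planned Day 1 post-administration change would be post − post = 0 for every eye, and every later change would be shifted by −(post − pre). SAP 9.2.2 plans that row as a result, so it must intend the pre-injection value. The two sections disagree when read literally.

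**The case against.** The strongest defence is that the inclusive count follows the plan's own definitions. Both insert-safety periods start on Day 1, and the primary objective covers insert safety from the day of treatment. Counting every observed elevation is the cautious choice for safety, and early rises belong in the Day 1 to Day 7 inserter evaluation. This stands. A reader might infer that the inclusive count is wrong and should be replaced. The documents do not support that, and replacement would drop observed elevations from the cumulative count.

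A reader might also infer that removing the Day 1 reading turns the Month 12 rate into a drug effect. It does not. All eyes receive the insert, no arm goes without it, and standard care continues throughout. Nor is the split between procedure and insert exact, since readings on Days 2 to 7 would stay in the added count.

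Much of the picture is reported elsewhere. The Day 1 change has its own row, and all IOP values are listed for about 30 eyes. IOP-lowering medication counts only after at least 7 days' use (SAP 7.1.3). IOP surgery (7.2.1) and elevated-IOP events (9.1.8) are tabulated separately. A careful reader could rebuild the missing count from the listing, but the table itself does not give it.

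The rates are assumed. The insert's dimensions in Protocol 10.1 give π × 0.185² × 3.5 ≈ 0.4 mm³, a small volume, so the low end of the range may apply. No rate in the table above is a forecast.

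On baseline, a reader might infer that every IOP change will be measured from a post-injection value. That is unlikely: the default yields where a section specifies otherwise, and 9.2.2 implies the pre-injection value. But it only implies it, and the written rule says something else.

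**Conclusion.** The point holds in a limited form. On plain wording, the > 21 mmHg count through Month 12 includes the reading taken 10 to 30 minutes after injection. It has no by-visit display, and the Day 7 count cannot be subtracted to recover later elevation. The size is unknown. The 3.5 to 27 point range rests on assumed rates and independence, and the excess can be zero. For the other four criteria the by-visit display covers much of the gap.

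The baseline rule in SAP section 4 conflicts, read literally, with the Day 1 change row in 9.2.2. This is a wording fault to correct, not evidence that the analysis would be run that way.

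The counts are descriptive, and the study's success criterion does not depend on them. The changes are still worth making, because the Month 12 table is meant to describe the insert and the changes need only existing data.

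**What to change.** In SAP 9.2.2:
- Keep the any-post-administration counts as planned.
- Add an ever-elevated count through Month 12 that excludes the Day 1 post-administration reading.
- Show that reading in its own row, by treatment group, for all five criteria, including > 21 mmHg.
- Define IOP baseline as the last non-missing value before injection, as an explicit exception to the default in SAP section 4.
- Add a table note that the counts are descriptive and, with no arm lacking the insert, do not estimate a drug effect.

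The cost is a few lines of SAP text, extra table rows and a small program change. No new data or visits are needed.

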5.2.2.3. Previous Human Experience with the FAI insert in uveitis subjects

The FAI insert is currently being evaluated in two phase 3 trials (PSV-FAI-001 and PSV-FAI-005) in subjects with chronic non-infectious uveitis affecting the posterior segment. In both studies, subjects are randomized (2:1) to receive either an intravitreal administration of the FAI insert or sham injection, respectively. Following treatment, subjects are being followed for three years. As of August 1, 2015, PSV-FAI-001 has completed enrollment (N=129) and is following subjects, and PSV-FAI-005 is actively enrolling subjects.

All study data are currently masked to treatment assignment. As of August 1, 2015, a total of 42 serious adverse events (SAEs) have been reported from both studies; none of these events was considered to be a suspected unexpected serious adverse reaction (SUSAR) that requires expedited safety reporting. Eight of the 42 SAE reports were non-ocular events judged by the investigator to be unrelated to study treatment. The remaining 34 SAE reports involved ocular events, of which 17 events were reported in the non-study eye and judged by the investigator to be unrelated to study treatment. The remaining 17 ocular events were reported in the study eye: 9 events were assessed by the investigator as not related to study treatment [sterile endophthalmitis (two events), uveitis (two events), macular edema (two events), cataract worsening, neovascular glaucoma, optic disc swelling], and 8 events were assessed by the investigator as possibly or probably related to study treatment [elevated IOP (three events), cataract (two events), hypotony (two events), and cystoid macular edema]. Additional information may be found in the IB.

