11.1.4. Protocol-Defined Ocular Serious Adverse Events

The following ocular events must be reported as SAEs during this trial:

- An AE which causes a decrease in visual acuity of \geq 30 letters, compared to the most recent previous measurement of visual acuity, lasting more than 1 hour
- An AE which causes a decrease in visual acuity to light perception or worse, lasting more than 1 hour
- An AE which requires surgical intervention (e.g., conventional surgery, vitreous tap or biopsy with intravitreal injection of anti-infectives, or laser or retinal cryopexy with gas) to prevent permanent loss of sight
- An AE which is associated with severe intraocular inflammation (i.e., 4.0 anterior chamber cell score, 4+ flare or 4+ vitritis)
- Two consecutive IOP measurements of 30 mmHg or higher taken at least 72 hours apart when a subject is already being treated with two glaucoma medications
- An IOP < 6 mmHg requiring medical intervention
- An AE which in the opinion of the Investigator requires medical or surgical intervention to prevent permanent loss of sight

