13.3. Safety

Safety endpoints include:

- Procedure-related adverse events, including: ocular adverse events (including IOP increase/decrease), clinically significant ocular changes, medications/procedures required to treat adverse events
- All other adverse events, including: ocular adverse events, IOP increase/decrease, medications/procedures required to control elevated/low IOP; development or worsening of cataract; cataract-related procedures; clinically significant ocular changes, systemic adverse events, medications/procedures required to treat adverse events

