7.1.2 Concomitant Medications

Concomitant medications are defined as those medications which are taken on or after the initiation of study treatment (Day 1). This includes medications which start prior to Day 1 but continue while the subject is on treatment.

Concomitant non-ocular medication will be summarized by treatment group for ATC level 1 term, ATC level 2 term and preferred term for the Safety population. The concomitant nonocular medication data will be also summarized for all subjects at the subject level. Summaries by treatment group will be based on the number of treated eyes; therefore a subject who has both eyes treated will be counted more than once, "repeating" and counting the non-ocular medication once for each treated eye. Percentages for the by treatment summaries will be based on the number of treated eyes and percentages for the total subjects summary will be based on the number of subjects who have at least one eye treated.

Concomitant ocular medication will be summarized by treatment group and for all treated eyes for each drug class and preferred term for the Safety population. Percentages will be based on the number of treated eyes.

An additional summary of concomitant medication for each of the specified reasons for medication (recurrence of uveitis, treatment emergent AE, increased IOP, cataract, other) will be reported as well.

7.1.3 **IOP Lowering Medications**

The number and percentage of eyes requiring IOP lowering medication to control elevated IOP will be summarized by treatment group and for all treated eyes. Any systemic medications will be summarized as received in both eyes. IOP lowering medications will be identified as those medications with a reason for medication of "Increased IOP". Incidence will be summarized through 12 months and for 3 month time intervals through 12 months.

The number of medications (one, two, \geq three) required to achieve adequate IOP control will also be included in the summary. IOP medications will be counted at the "ingredient" level. For example, if the subject is receiving COSOPT (which contains two ingredients TIMOLOL MALEATE and DORZOLAMIDE HYDROCHLORIDE) and TIMOLOL MALEATE at the same time, the subject will be included in analysis as receiving two medications.

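### IOP decrease is a named safety endpoint, but SAP 9.2.2 counts eyes only against upward thresholds, so a low reading neither treated nor reported as an adverse event is not counted by inserter

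*SAP*

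**What the plan says.** SAP 3.2 defines inserter safety over Day 1 to Day 7 as "Ocular adverse events, including: procedure-related adverse events, IOP increase/decrease, medications/procedures required to treat adverse events, clinically significant ocular changes". For the insert, through Day 7 and through Month 12, it lists "IOP increase/decrease, medications/procedures required to control elevated/low IOP, development or worsening of cataract". Protocol 13.3 and the synopsis carry the same content. Both directions of IOP change are therefore named, and so is treatment for low pressure after the insert.

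SAP 9.2.2 plans three IOP tables by treatment group: observed values and changes from baseline; eyes above 21 mmHg at any time after administration; and "the number and percentage of eyes with an IOP measurement meeting any of the IOP elevation criteria at any post-administration assessment" and by visit. The elevation criteria are a rise above 5 mmHg, a rise of 12 mmHg or more, a value above 25 mmHg and a value above 30 mmHg.

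The treatment summaries follow the same direction. In SAP 7.1.3, "The number and percentage of eyes requiring IOP lowering medication to control elevated IOP will be summarized", and SAP 7.2.1 does likewise for surgery. The pressure terms in SAP 9.1.8 are for raised IOP. The one downward numeric criterion among the reportable events is in Protocol 11.1.4, repeated in SAP 9.1.4: "An IOP < 6 mmHg requiring medical intervention".

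**The concern.** Safety of the Mk II inserter through 7 days is part of the primary objective (Protocol 6.1). The two inserters differ in needle gauge and wall (Protocol 5.5 and 5.6), and IOP is already measured 10 to 30 minutes after injection and at every visit. SAP 9.1.9 itself gives decreased IOP as an example of an event that could be procedure-related. A reader of the safety tables would expect to learn how many eyes in each inserter group had low pressure. The threshold tables answer that question for high pressure only.

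The adverse event route does not fully make up for this. Protocol 11.1.3 obliges a report for defined rises and sets no criterion for a fall. Whether an untreated low reading becomes an adverse event is then largely the Investigator's judgement. That person knows which inserter was used, because only subjects are masked (Protocol 7.1), and they or a designee make all later assessments (Protocol 7.5).

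**Working it through.** **1. Where a low reading can surface.**

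| Planned output | Content | Low IOP included? |
|---|---|---|
| SAP 9.2.2 threshold counts | >21; rise >5; rise ≥12; >25; >30 mmHg | No: 5 upward, 0 downward |
| SAP 9.2.2 continuous table | Values and changes by group, at scheduled visits and after injection on Day 1; SAP 4 includes the minimum | Yes, as summary statistics |
| SAP 7.1.3 and 7.2.1 | Medication or surgery for elevated IOP | No |
| SAP 7.1.2 and 7.2, by reason | Uveitis recurrence, adverse event, increased IOP, cataract, other | Only inside the adverse event or other categories |
| SAP 9.1.8 | Cataract and raised-IOP terms; complications of IOP-lowering treatment and of cataract surgery | Only as a reported complication of such treatment |
| SAP 9.1.1, protocol-defined events | IOP criterion is a rise | No |
| SAP 9.1.1 by preferred term; 9.1.9 | Reported events, by group | Yes, if reported |
| SAP 9.1.4 | IOP below 6 mmHg needing intervention | Yes, if treated |
| Listing | All IOP values | Yes, uncounted |

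**2. Can the continuous table stand in for a count?** Take two constructed groups of 10 eyes (mmHg):

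- A = {4, 6, 6, 7, 8, 13, 16, 16, 20, 20}
- B = {4, 4, 5, 10, 10, 11, 16, 18, 18, 20}

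Both sum to 116, so the mean is 11.6. Both have a sum of squares of 1682, so the SD is √[(1682 − 116²/10)/9] = √(336.4/9) = 6.1. The medians are (8+13)/2 and (10+11)/2, both 10.5. Both have minimum 4 and maximum 20. Every planned statistic agrees, yet A has 1 eye below 6 mmHg and B has 3. The minimum shows whether any eye was low at that visit, but not how many.

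**3. Which readings enter the table?** By-visit tables use only readings assigned to a window (SAP 4). The Day 7 window is study days 4 to 10, so an unscheduled reading on Day 2 or 3 enters no by-visit table. Within a window, a scheduled reading displaces unscheduled ones. A 4 mmHg reading at an unscheduled Day 5 visit, recovered by the scheduled Day 7 visit, would be absent even from the minimum. The high-IOP counts, as worded, take any reading after administration.

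**4. What a low-IOP count would show.** The plan gives no figure for low IOP. Its stated precision does reproduce with the exact (Clopper-Pearson) method: 10/20 gives 27.2% to 72.8%, and 5/10 gives 18.7% to 81.3%. The same method gives:

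| Eyes below 6 mmHg | Mk II (n = 20) | Mk I (n = 10) |
|---|---|---|
| 0 | 0% (0 to 16.8) | 0% (0 to 30.8) |
| 1 | 5% (0.1 to 24.9) | 10% (0.3 to 44.5) |
| 2 | 10% (1.2 to 31.7) | 20% (2.5 to 55.6) |

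The chance of seeing at least one such eye is 1 − (1 − p)ⁿ. At assumed true rates of 2%, 5%, 10% and 20% this is 33%, 64%, 88% and 99% with n = 20, and 18%, 40%, 65% and 89% with n = 10. With no low eyes in the other group, Fisher's exact test would need 3/10 on Mk I (p = 0.030) or 8/20 on Mk II (p = 0.029) to fall below 0.05. The count would be descriptive only.

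**The case against.** The strongest reply is that the endpoint is framed as adverse events, and the adverse event analyses run in both directions. SAP 9.1.9 reviews events with onset within 7 days and tabulates the related ones as in 9.1.1, with no condition that they were treated. Protocol 11.1.1 counts any unfavourable sign as an adverse event, and Protocol 11.4.3 asks for significant examination changes to be recorded. The by-group IOP table shows falls as well as rises, and every value is listed.

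Much of this stands. A reader might infer that low pressure is never compared between inserters, that every planned IOP count looks upward, or that the IOP tables can show harm in one direction only. The documents do not support any of these: the continuous table, 9.1.1, 9.1.9 and 9.1.4 all contradict them. A reader might also lean on the sponsor's earlier experience (Protocol 5.2.2.3), where the 8 study-eye ocular serious events judged possibly or probably related were "elevated IOP (three events), cataract (two events), hypotony (two events), and cystoid macular edema". Those data are masked, pool insert and sham, and give no incidence denominator. The events were also serious, so their like would be tabulated here anyway. They show that hypotony is a relevant term, but say nothing about how often untreated low readings occur. Nor do the documents say that a fall in pressure measures the needle difference; Protocol 5.3 gives ease of use as the expected gain.

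What the reply does not reach is the unreported reading. SAP 9.1.9 reviews recorded events, not IOP values, and what is significant remains a judgement.

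**Conclusion.** The point holds in a narrow form. An untreated low IOP reading that is not reported as an adverse event has no count by inserter, and if taken at an unscheduled visit it can be missing from the by-visit table and appear only in a listing. Treatment for low IOP, a named endpoint for the insert, has no row of its own. This rests on reading the SAP 9.2.2 elevation counts as including unscheduled assessments, which their wording allows, and on no separate table shells adding a low-IOP row.

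The impact is minor. It concerns descriptive reporting in about 30 eyes, in a study the SAP says is not powered to separate the inserters, and it does not touch the success rule. It is a cheap improvement.

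**What to change.** - **SAP 9.2.2:** add, by inserter, the number and percentage of eyes with IOP below 6 mmHg at any time after administration and by visit, through Day 7 and through Month 12. The value already appears in exclusion criterion 9, Protocol 11.1.4 and SAP 9.1.4. It would serve here as a reporting cut-off only, not a management rule.
- **SAP 7.1.2 and 7.2:** add a row for eyes given medication or a procedure for low IOP. The listed reasons have no such category, so entries under adverse event or other would need a text review, as SAP 7.2.1 already plans for IOP surgeries recorded under other.
- **SAP 9.1.8:** add hypotony and decreased-IOP preferred terms to the special-interest events.

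A row for falls of more than 5 mmHg is optional at most. It would flag a change from 20 to 14 mmHg, which stays inside the 10 to 21 mmHg range the protocol calls normal.

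The cost is a few table rows and a short manual review, with no new measurements and no change in sample size. The downside is that transient low readings will be counted, so the safety tables will look slightly less favourable.
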